Appendix E. Schedule of Extended Access Phase*

Procedure	W108 D1	W120 D1	W132 D1	W144 D1	W156 D1	W168 D1	W180 D1	W192 D1	W204 D1	W216/ Final Visit	30 Day Safety Visit ^d	Post Treatment Follow up ^e
Vital signs**	X									X	X	
Physical Examination ^{a**}	X									X	X	
ECOG Performance Status**	X									X	X	
Hematology/Chemistry***	X									X	X	
Adverse Event/Concomitant Medication Assessment	X	X	X	X	X	X	X	X	X	X	X	X
Venetoclax dispensation and accountability****	X	X	X	X	X	X	X	X	X			
Collection of Survival Information ^b	X	X	X	X	X	X	X	X	X	X	X	X
Quality of Life Questionnaires (EORTC QLQ-30, EORTC QLQ-CLL16, EQ-5D-5L) ^c	X											

* In countries where venetoclax is not commercially available, subjects who continue to derive benefit after 2 years of treatment may be able to extend their treatment for up to 2 additional years. AbbVie will work with the investigator on a case by case basis to consider the potential continuation of venetoclax therapy.

** Within 72 hours before or after scheduled visit.

*** Within 72 hours prior to scheduled visit.

**** The visit window for scheduled visits is \pm 2 days.

a. Refer to Section 5.3.1.1 Physical Examination, for more details.

b. Survival information includes i.e., the date/cause of death, post treatment cancer therapies, etc.

- c. The Quality of Life Questionnaires should be administered and completed prior to any other study procedures being performed at these visits. Refer to Section [5.3.2.2.1](#) Health Economic and Patient-Reported Outcome Measures, for further information.
- d. 30-Day Safety Follow-up visit should occur approximately 30 days (\pm 3 days) after the last dose of venetoclax.
- e. Upon discontinuation of study drug treatment, survival information (i.e., the date/cause of death, post treatment cancer therapies, etc.) will be collected every 6 months (\pm 7 days) for a period of 2 years

Appendix F. Definitions of Laboratory and Clinical Tumor Lysis Syndrome

Metabolic Abnormality	Criteria for Classification of Laboratory Tumor Lysis Syndrome	Criteria for Classification of Clinical Tumor Lysis Syndrome
Hyperruricemia	Uric acid > 8.0 mg/dL (475.8 µmol/liter) in adults or above the upper limit of the normal range for age in children	
Hyperphosphatemia	Phosphorus > 4.5 mg/dL (1.5 mmol/liter) in adults or > 6.5 mg/dL (2.1 mmol/liter) in children	
Hyperkalemia	Potassium > 6.0 mmol/liter	Cardiac dysrhythmia or sudden death probably or definitely caused by hyperkalemia
Hypocalcemia	Corrected calcium < 7.0 mg/dL (1.75 mmol/liter) or ionized calcium < 1.12 (0.3 mmol/liter) [†]	Cardiac dysrhythmia, sudden death, seizure, neuromuscular irritability (tetany, paresthesias, muscle twitching, carpopedal spasm, Trousseau's sign, Chvostek's sign, laryngospasm, or bronchospasm), hypotension, or heart failure probably or definitely caused by hypocalcemia
Acute kidney injury [‡]	Not applicable	Increase in the serum creatinine level of 0.3 mg/dL (26.5 µmol/liter) (or a single value > 1.5 times the upper limit of the age-appropriate normal range if no baseline creatinine measurement is available) or the presence of oliguria, defined as an average urine output < 0.5 mL/kg/hr for 6 hrs

[†] The corrected calcium level in milligrams per deciliter = measured calcium level in milligrams per deciliter + 0.8 × (4-albumin in grams per deciliter).

[‡] Acute kidney injury is defined as an increase in the creatinine level of at least 0.3 mg per deciliter (26.5 µmol per liter) or a period of oliguria lasting 6 hours or more. By definition, if acute kidney injury is present, the subject has clinical tumor lysis syndrome. Data about acute kidney injury from Levin et al.

Note: In laboratory tumor lysis syndrome, two or more metabolic abnormalities must be present during the same 24-hour period within 3 days before the start of therapy or up to 7 afterward. Clinical tumor lysis syndrome requires the presence of laboratory tumor lysis syndrome plus an increased creatinine level, seizures, cardiac dysrhythmia, or death.

Appendix G. Recommendations for Initial Management of Electrolyte Abnormalities and Prevention of Tumor Lysis Syndrome (TLS)

Section 1: First Dose of Venetoclax or Dose Escalation

- Within the first 24 hours after either the first dose or dose escalation, if any laboratory criteria below are met, the subject should be hospitalized for monitoring and the investigator notified. No additional venetoclax doses should be administered until resolution. Rapidly rising serum potassium is a medical emergency.
- Nephrology (or other acute dialysis service) should be contacted/consulted (per institutional standards to ensure emergency dialysis is available) on admission for any subject hospitalized prophylactically or in response to laboratory changes.
- IV fluids (e.g., D5 1/2 normal saline) should be initiated at a rate of at least 1 mL/kg/hr rounded to the nearest 10 mL (target 150 to 200 mL/hr; not < 50 mL/hr). Modification of fluid rate should also be considered for individuals with specific medical needs.
- Monitor for symptoms or signs of TLS (e.g., fever, chills, tachycardia, nausea, vomiting, diarrhea, diaphoresis, hypotension, muscle aches, weakness, paresthesias, mental status changes, confusion and seizures). If any clinical features are observed, recheck potassium, phosphorus, uric acid, calcium and creatinine within 1 hour STAT.
- Vital signs should be taken at time of all blood draws or any intervention.
- The management recommendations below focus on the minimum initial responses required. If a diagnosis of TLS is established, ongoing intensive monitoring and multi-disciplinary management will be per institutional protocols.

In addition to the recommendations in the table below, for subjects receiving the first dose of venetoclax.

- For potassium increase ≥ 0.5 mmol/L from baseline, or any value > 5.0 mmol/L, recheck potassium, phosphorus, uric acid, calcium and creatinine within 1 hour STAT and follow first guideline.
- For phosphorus increase of > 0.5 mg/dL AND > 4.5 mg/dL, administer phosphate binder and recheck potassium, phosphorus, uric acid, calcium and creatinine within 1 hour STAT.

Abnormality	Management Recommendations
Hyperkalemia (Including Rapidly Rising Potassium)	
Potassium ≥ 0.5 mmol/L increase from prior value (even if potassium within normal limits [WNL])	
 • Recheck potassium, phosphorus, uric acid, calcium and creatinine in 1 hour STAT. If further ≥ 0.2 mmol/L increase in potassium, but still $<$ upper limit of normal (ULN), manage as per potassium \geq ULN. Otherwise recheck in 1 hour. • Resume per protocol testing if change in potassium is < 0.2 mmol/L, and potassium $<$ ULN, and no other evidence of tumor lysis. • At the discretion of the investigator, may recheck prior to hospitalization. If stable or decreased, and still WNL, hospitalization is at the discretion of the investigator. Potassium, phosphorus, uric acid, calcium and creatinine must be rechecked within 24 hours.
Potassium $>$ upper limit of normal	
 • Perform STAT ECG and commence telemetry. • Nephrology (or other acute dialysis service) notification with consideration of initiating dialysis. • Administer Kayexalate 60 g (or Resonium A 60 g). • Administer furosemide 20 mg IV $\times 1$. • Administer calcium gluconate 100 to 200 mg/kg IV slowly if there is ECG/telemetry evidence of life-threatening arrhythmias. • Recheck potassium, phosphorus, uric acid, calcium and creatinine in 1 hour STAT. 
 ○ If potassium $<$ ULN 1 hour later, repeat potassium, phosphorus, uric acid, calcium and creatinine 1, 2 and 4 hrs., if no other evidence of tumor lysis.

Abnormality	Management Recommendations
Hyperkalemia (Including Rapidly Rising Potassium) (continued)	
Potassium ≥ 6.0 mmol/L (6.0 mEq/L) and/or symptomatic (e.g., muscle cramps, weakness, paresthesias, nausea, vomiting, diarrhea)	
 • Perform STAT ECG and commence telemetry. • Nephrology (or other acute dialysis service) assessment with consideration of initiating dialysis. • Administer Kayexalate 60 g (or Resonium A 60 g). • Administer furosemide 20 mg IV \times 1. • Administer insulin 0.1 U/kg IV + D25 2 mL/kg IV. • Administer sodium bicarbonate 1 to 2 mEq/kg IV push. 
 ○ If sodium bicarbonate is used, rasburicase should not be used as this may exacerbate calcium phosphate precipitation. • Administer calcium gluconate 100 to 200 mg/kg IV slowly if there is ECG/telemetry evidence of life-threatening arrhythmias. Do not administer in same IV line as sodium bicarbonate. • Recheck potassium, phosphorus, uric acid, calcium and creatinine every hour STAT.
Hyperuricemia	
Uric acid ≥ 8.0 mg/dL (476 μ mol/L)	
 • Consider rasburicase* (dose based on local guidelines and/or institutional standards). 
 ○ If rasburicase is used, sodium bicarbonate should not be used as this may exacerbate calcium phosphate precipitation. • Recheck potassium, phosphorus, uric acid, calcium and creatinine in 1 hr STAT.
Hyperuricemia	
Uric acid ≥ 10 mg/dL (595 μ mol/L)	
 • Administer rasburicase* (dose based on local guidelines and/or institutional standards). 
 ○ When rasburicase is used, sodium bicarbonate should not be used as this may exacerbate calcium phosphate precipitation. • Notify nephrology (or other acute dialysis service). • Recheck potassium, phosphorus, uric acid, calcium and creatinine in 1 hour STAT. 
 ○ If uric acid < 8.0 mg/dL 1 hour later, repeat potassium, phosphorus, uric acid, calcium and creatinine 2 and 4 hrs., later, if no other evidence of tumor lysis.
OR	
Uric acid ≥ 8.0 mg/dL (476 μ mol/L) with 25% increase and creatinine increase ≥ 0.3 mg/dL (≥ 0.027 mmol/L) from pre-dose level	

Abnormality	Management Recommendations
Hypocalcemia	
Calcium \leq 7.0 mg/dL (1.75 mmol/L)	
 • Administer calcium gluconate 50 to 100 mg/kg IV slowly with ECG monitoring. • Telemetry. • Recheck potassium, phosphorus, uric acid, calcium and creatinine in 1 hr STAT. 
 ○ If calcium normalized 1 hour later, repeat potassium, phosphorus, uric acid, calcium and creatinine 2 and 4 hrs., later, if no other evidence of tumor lysis. • Calculate corrected calcium and check ionized calcium if albumin low.

AND
 
Subject symptomatic (e.g., muscle cramps, hypotension, tetany, cardiac arrhythmias)
	
Hyperphosphatemia	
Phosphorus \geq 5.0 mg/dL (1.615 mmol/L) with \geq 0.5 mg/dL (0.16 mmol/L) increase	
 • Administer a phosphate binder (e.g., aluminum hydroxide, calcium carbonate, sevelamer hydroxide, or lanthanum carbonate). • Nephrology (or other acute dialysis service) notification (dialysis required for phosphorus \geq 10 mg/dL). • Recheck potassium, phosphorus, uric acid, calcium and creatinine in 1 hr STAT. 
 ○ If phosphorus $<$ 5.0 mg/dL 1 hour later, repeat potassium, phosphorus, uric acid, calcium and creatinine 2 and 4 hrs., later, if no other evidence of tumor lysis.
Creatinine	
Increase \geq 25% from baseline	
 • Start or increase rate of IV fluids. • Recheck potassium, phosphorus, uric acid, calcium and creatinine in 1 to 2 hours STAT.

* Check rasburicase label for contraindications.

Section 2: Ongoing Dosing of Venetoclax

Management of electrolyte changes from last value at intervals $>$ 24 hours after either the first dose or dose escalation (e.g., 48 or 72 hours) are as below.

Note: If the subject is hospitalized, no additional venetoclax doses should be administered until resolution.

- For potassium, admit subject for any increase ≥ 1.0 mmol/L (1.0 mEq/L), or any level $>$ upper limit of normal.
 - Refer to the management guidelines for electrolyte changes observed within the first 24 hours after either the first dose or dose escalation (see prior table).
- If a smaller potassium increase is observed that does not meet the criteria for admission above, recheck potassium, phosphorus, uric acid, calcium and creatinine in 24 hours and confirm no evidence of tumor lysis prior to further venetoclax dosing.
- For uric acid, calcium, phosphorus and creatinine, refer to the management guidelines for electrolyte changes observed within the first 24 hours after either the first dose or dose escalation (see prior table).

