5.5.4 Selection and Timing of Dose for Each Subject

Venetoclax will be administered orally once daily (QD) beginning with a dose-titration phase. As shown in [Figure 2](#), the initial venetoclax dose is 20 mg QD. After 1 week of treatment at 20 mg QD, the dose will be escalated to 50 mg QD followed by subsequent increases, each after 1 week, to 100 mg QD, 200 mg QD and the maximum dose of 400 mg QD. The maximum dose of venetoclax for this protocol will not exceed 400 mg per day. The 5-week dose-titration phase is designed to gradually reduce tumor burden (debulk) and decrease the risk of tumor lysis syndrome. All study subjects will be categorized at Screening according to their risk for developing TLS. Their dose management, including during the dose-titration phase, will be conducted in accordance with their risk for developing TLS (Section [6.1.9.1](#)) and may include dose delay and/or dose reduction as required for prophylaxis and management of TLS.

Figure 2. 5-Week Dose-Titration Schematic

*Dose escalation will occur in accordance with specific risk-based TLS prophylaxis and monitoring measures that may include dose delay and/or dose reduction.

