6.1.9 Toxicity Management

6.1.9.1 Prophylaxis and Management of Tumor Lysis Syndrome

Venetoclax can cause rapid reduction in tumor and thus poses a risk for TLS in the initial 5-week dose-titration phase. Changes in electrolytes consistent with TLS that require prompt management can occur as early as 6 to 8 hours following the first dose of venetoclax and at each dose increase.

Risk Assessment for tumor lysis syndrome: The risk of TLS is a continuum based on multiple factors, including tumor burden and comorbidities. Subjects with high tumor burden (e.g., any lymph node with a diameter ≥ 5 cm or high absolute lymphocyte count [ALC $> 25 \times 10^9/L$]) are a greater risk of TLS. Reduced renal function (estimated creatinine clearance [eCrCl] < 80 mL/min) further increases the risk. The risk may decrease as tumor burden decreases with venetoclax treatment.

Additional comorbidities may further increase the risk for TLS.

Prior to initiating venetoclax, tumor burden assessment, including radiographic evaluation (e.g., refer to Section 5.3.1.1 Study Procedures – Disease Assessment) must be performed for all subjects during Screening. The full blood chemistry/hematology panel (refer to Table 4 Clinical Laboratory Tests) should be performed in all subjects during the Screening period in order to assess eligibility and to correct pre-existing abnormalities.

If the full chemistry/hematology panel was assessed more than 72 hours prior to the 1st dose of venetoclax, an additional full lab panel should be performed and reviewed within 72 hours prior to dosing in order to make a treatment decision.

Prophylaxis for tumor lysis syndrome: The prophylaxis measures listed below should be followed. More intensive measures (including hospitalization) should be employed as overall risk increases:

Hydration: Subjects should be adequately hydrated prior to starting treatment with venetoclax and during the dose-titration phase. The recommended volume is 1.5 to 2.0 L (approximately 6 to 8 glasses) of water each day. Subjects should be instructed to drink water starting 2 days before and on the day of the first dose, and every time the dose is increased. Intravenous (IV) fluids should be administered as indicated based on overall risk of TLS or for those who cannot maintain an adequate level of oral hydration. For subjects for whom volume overload is considered a significant risk, hospitalization should be considered.

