Anti-hyperuricemic agents: Anti-hyperuricemic agents should be administered 2 to 3 days prior to starting treatment with venetoclax and may be continued through the titration phase.

Laboratory Assessments:

PRE-DOSE LABS:

Prior to the initial dose of venetoclax:

- During the Screening Period: For all subjects, the chemistry/hematology panel (see [Table 4](#) Clinical Laboratory Tests) is required.
 - Pre-existing abnormalities should be corrected.
- Within 72 hours of Week 1/Day 1: If the screening labs were more than 72 hours before the planned first dose, the chemistry/hematology panel should be repeated. These results should be reviewed before dosing.
 - Labs should be assessed and pre-existing abnormalities should be corrected.
- On the day of Week 1/Day 1: Before dosing, the chemistry/hematology panel should be drawn. The results of the labs drawn on Week 1 Day 1 need to be reviewed prior to dosing **IF** an additional lab within 72 hours of the initial dose at Week 1 Day 1 was not drawn **AND** reviewed.

Prior to each subsequent dose increase, for all subjects:

- Within 72 hours of each subsequent dose increase: The chemistry/hematology panel should be repeated. The results should be reviewed prior to dose increasing.
- Prior to dosing, on the day of each subsequent dose increase: Before dosing, the chemistry/hematology panel should be drawn. The results of the labs drawn on Day 1 of each dose increase need to be reviewed prior to dosing **IF** an additional lab draw within 72 hours of the dose increase was not drawn AND reviewed.

POST-DOSE LABS:

For all subjects, the chemistry/hematology panel (refer to Table 4 Clinical Laboratory Tests) should be monitored at 6 to 8 hours and at 24 hours* after the first dose of venetoclax (20 mg) and after the first dose increase (50 mg). Electrolyte abnormalities should be corrected promptly. The next venetoclax doses (Day 2 20 mg venetoclax dose and Day 2 50 mg venetoclax dose) should not be administered until the 24-hour* lab results have been evaluated. Electrolyte abnormalities should be corrected promptly. For subjects who continue to be at risk of TLS, the same lab monitoring schedule (i.e., 6 to 8 hour and 24-hr post dose) should be followed at the subsequent dose increases.

This monitoring is also recommended during the re-initiation of the therapy after a dose interruption.

*All 24 hour post-dose laboratory assessments may be taken within a 2 hour window, if necessary.

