6.1.9.2 Dose Modifications Based on Toxicities

Dosing interruption and/or dose reduction may be required. See [Table 7](#) for dose modifications for hematologic and other toxicities related to venetoclax. For subjects who have had a dosing interruption greater than 1 week during the first 5 weeks of dose titration or greater than 2 weeks when at the daily dose of 400 mg, TLS risk should be reassessed to determine if restarting at a reduced dose is necessary (e.g., all or some levels of the dose titration).

Tumor Lysis Syndrome

If a subject experiences blood chemistry changes suggestive of TLS, the following day's venetoclax dose should be withheld. If resolved within 24 to 48 hours of last dose, treatment with venetoclax can be resumed at the same dose. For events of clinical TLS or blood chemistry changes requiring more than 48 hours to resolve, treatment should be resumed at a reduced dose ([Table 7](#) and [Table 8](#)). When resuming treatment with venetoclax after interruption due to TLS, the instructions for Prophylaxis for tumor lysis syndrome should be followed.

Other Toxicities

Treatment with venetoclax should be withheld for any grade 3 or 4 non-haematological, grade 3 or 4 neutropenia with infection or fever, or grade 4 haematological toxicities, except lymphopenia. To reduce the risk of infection associated with neutropenia, granulocyte-colony stimulating factor (G-CSF) may be administered with venetoclax if clinically indicated. Once the toxicity has resolved to grade 1 or baseline level (recovery), therapy with venetoclax may be restarted at the same dose. If the toxicity recurs, and for any subsequent occurrences, the dose reduction guidelines in [Table 7](#) and [Table 8](#) should be followed when resuming treatment with venetoclax following resolution. A larger dose reduction may occur at the discretion of the investigator. For subjects who require dose reductions to less than 100 mg for more than 2 weeks, due to adverse events, discontinuation of venetoclax should be considered.

Table 7. Recommended Dose Modifications for Toxicities

Event	Occurrence	Action
Tumor Lysis Syndrome		
Blood chemistry changes or symptoms suggestive of TLS	Any	Withhold the next day's dose. If resolved within 24 – 48 hours of last dose, resume at the same dose.
		For any blood chemistry changes requiring more than 48 hours to resolve, resume at a reduced dose (Table 8)

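### The Appendix F window for laboratory TLS closes about a week after the first dose, so read literally it leaves out the 100, 200 and 400 mg steps, where the protocol still expects TLS

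*Protocol*

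**What the plan says.** **Definition.** The Note under the Protocol Appendix F table requires two or more metabolic abnormalities "during the same 24-hour period within 3 days before the start of therapy or up to 7 afterward". Its next sentence makes the clinical form depend on the laboratory form: "Clinical tumor lysis syndrome requires the presence of laboratory tumor lysis syndrome plus an increased creatinine level", or seizures, dysrhythmia or death. Nothing else in the protocol or SAP restarts or extends this window.

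**Dosing.** Section 5.5.4 starts at 20 mg and moves to 50 mg after a week, "followed by subsequent increases, each after 1 week, to 100 mg QD, 200 mg QD and the maximum dose of 400 mg QD".

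**Where risk is placed.** Section 6.1.9.1 warns of electrolyte changes "following the first dose of venetoclax and at each dose increase". It requires draws at 6 to 8 hours and at 24 hours for everyone after the first 20 mg and first 50 mg doses. At later increases, for "subjects who continue to be at risk of TLS, the same lab monitoring schedule" applies. It adds: "This monitoring is also recommended during the re-initiation of the therapy after a dose interruption". The management rules in Appendix G, Section 1, are triggered "Within the first 24 hours after either the first dose or dose escalation".

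**Restart rules.** Section 6.1.9.2 withholds the next day's dose for chemistry changes that suggest TLS. "If resolved within 24 to 48 hours of last dose, treatment with venetoclax can be resumed at the same dose". Clinical TLS, or changes that take more than 48 hours to resolve, lead to a reduced dose under Table 8. Footnote a of Table 7 defines clinical TLS as laboratory TLS with clinical consequences. Only Appendix F defines laboratory TLS.

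**The concern.** The definition is tied to the start of therapy, but the drug is escalated over five weeks and the protocol expects TLS at each escalation. A site that applies the Note literally could not classify an event at the 100, 200 or 400 mg step as laboratory TLS. Through footnote a of Table 7, it could then not call the event clinical TLS by that route either. Section 6.1.9.2 restarts clinical TLS at a reduced dose but allows the same dose for chemistry changes that resolve quickly, so the label can affect the dose. TLS is an adverse event of special interest in this protocol (Section 6.1.1.4), and the Introduction reports two deaths in the setting of TLS before the titration regimen was adopted.

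**Working it through.** **Inputs.** The window runs from 3 days before to 7 after the start of therapy (Appendix F). The unit of the 7 is missing; days is assumed, carried over from the 3 days. The first dose is Day 1. Steps are weekly (Section 5.5.4), and SAP Table 2 agrees, with Week 4 Day 1 as Day 22. Post-dose draws are at 6 to 8 hours and at 24 hours (Section 6.1.9.1).

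**Window end.** Day 1 + 7 days = Day 8.

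**Step days.** 1 + 7 × (week − 1).

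| Step | Dose day | 6–8 h draw | 24 h draw | Who is drawn |
|---|---|---|---|---|
| 20 mg | 1 | Day 1, inside | Day 2, inside | all |
| 50 mg | 8 | Day 8, inside | Day 9, outside | all |
| 100 mg | 15 | Day 15, outside | Day 16, outside | still at risk |
| 200 mg | 22 | Day 22, outside | Day 23, outside | still at risk |
| 400 mg | 29 | Day 29, outside | Day 30, outside | still at risk |

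Three of five steps lie wholly outside the window. Of the draws required for all subjects, 3 of 4 are inside; of those for subjects still at risk, 0 of 6.

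**Sensitivity to the unit.** In elapsed time the limit is 7 × 24 = 168 h. The 50 mg dose falls at 168 h and its first draw at 174 to 176 h, which is outside, so 2 of 4 are inside. Only a reading in weeks (7 × 7 = 49 days) would cover every step, and nothing in the text supports it.

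**Where the label matters.** For a later-step event that meets the laboratory criteria:

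- Changes that take more than 48 hours to resolve: reduced dose with or without the label.
- Acute kidney injury: an Appendix F footnote makes this clinical TLS by definition and sets no window, so the reduced dose applies.
- Death: no restart.
- Another clinical consequence, such as dysrhythmia or seizure, resolved within 24 to 48 hours of the last dose: the same dose is allowed without the label and a reduced dose applies with it.

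Only the last case is affected. The doses at stake come from Table 8:

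| Dose at interruption | Same | Reduced | Difference |
|---|---|---|---|
| 50 mg (Day 9 draw) | 50 | 20 | (50 − 20)/50 = 60% |
| 100 mg | 100 | 50 | (100 − 50)/100 = 50% |
| 200 mg | 200 | 100 | (200 − 100)/200 = 50% |
| 400 mg | 400 | 300 | (400 − 300)/400 = 25% |

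**Example.** The last dose is 400 mg on Day 29. At the Day 30 draw, potassium is 6.2 mmol/L (criterion above 6.0) and phosphorus 5.0 mg/dL (criterion above 4.5), with a dysrhythmia caused by the hyperkalemia. All resolves by 48 hours after the Day 29 dose. Day 30 is outside the window, so a literal reader does not call it TLS and may restart at 400 mg. With the window anchored to the Day 29 increase it is clinical TLS, and the restart dose is 300 mg.

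**Check of the fix.** Windows from 3 days before to 7 days after each step end on Days 8, 15, 22, 29 and 36 and overlap, so all 10 draws are inside.

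**The case against.** The best reply is that the Note has almost no operative force. No TLS section cites Appendix F; its one citation in the body, in Section 9.2, is for investigator responsibilities. Footnote a of Table 7 states no window. To reach a different dose, a site would have to find the Note, apply it strictly, deny the TLS label to a hyperkalemic dysrhythmia just after an escalation, and then choose a restart option that is only permissive, in a table headed as recommended. The missing unit can pass as ordinary ellipsis. Appendix F also stands under a citation to a published general classification, and whether its wording follows that source cannot be checked here.

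A reader might infer that TLS at later steps goes unmanaged. The documents do not support that: dose holding, monitoring of at-risk subjects, Appendix G management and the reduction for changes lasting over 48 hours all apply without the label. Nor do they support the inference that every later-step event with clinical consequences is lost, because of the kidney-injury footnote. A third inference would be that the SAP under-counts TLS by design. Its searches (SAP Table 3) use MedDRA terms and no Appendix F window. A count could move only if a site reported a different adverse event term because of the Note.

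These points make the effect small. They do not remove the contradiction. Neither the Table 7 row for chemistry changes or symptoms nor the row for a first Grade 3 or 4 non-hematologic toxicity forces a reduced dose in the affected case.

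**Conclusion.** The point holds in a narrow form. Read literally, the Note excludes three of five dose steps, the Day 9 draw and any re-initiation after Day 8, against the rest of the protocol. The one decision it could change is the restart dose after a later-step, non-renal clinical event that resolves within 24 to 48 hours of the last dose. There the two permitted readings differ by 25% to 60% of the dose.

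This assumes that the unit is days, that escalation is weekly without delay (a delay moves the steps further outside), and that a site applies the Note strictly. The frequency cannot be computed. The Introduction reports no clinical or laboratory TLS in the monotherapy analysis after prophylaxis was introduced, and no clinical TLS under the approach evaluated since May 2014, but it gives no denominators. Such events should be rare. Severity is minor; confidence is high on the text and lower on any practical consequence.

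**What to change.** Change the timing in the first sentence of the Appendix F Note to: *within 3 days before or up to 7 days after the first dose, each dose increase, or each re-initiation after an interruption*. Leave Tables 7 and 8, Appendix G, the kidney-injury footnote and the SAP searches as they are. Do not add a cross-reference from Table 7 to Appendix F unless the Note's clinical list (creatinine, seizures, dysrhythmia, death) is first aligned with the longer list in the appendix's clinical column.

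The cost is one protocol sentence, with no new visits, data or programming. The downside is that slightly more later-step events may be labelled TLS and restarted at a reduced dose.
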